8. PREMATURE WITHDRAWAL OF SUBJECTS

Subjects have the right to withdraw from the study at any time for any reason. The investigator also has the right to withdraw a subject from the study, if he/she seems it to be in the subject's best interest. It is recognized that an excessive rate of withdrawals may render the study uninterrupted and, therefore, it is desirable to avoid unnecessary withdrawals.

While lack of venous access is not anticipated as a major problem, a subject will be withdrawn from the trial if the investigator cannot find venous access during the treatment study visits (Visits 1-16).

Noncompliance with study treatment/ offloading in a manner that interrupt treatment and delay healing, according to principal investigator judgment

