1.2. Study Design

The study is a prospective, single arm, multicenter efficacy study, consisting of 60 subjects who will complete the study (note: if any patients are lost to follow-up or withdrawn, enrollment will increase to compensate for loss of these subjects). The subjects will receive up to 16 RD1 applications. In case of complete healing, subject will be called for one confirmatory visit two weeks later or before discharge from the SNF (the earlier of the two). Subject data will be kept in each site's records.

All diabetic subjects' glycemic management will be performed by a qualified physician. All subjects will have wound care specialist or wound surgeon or dermatologist involved in their wound care

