4. STOPPING RULES

4.1. Individuals

4.1.1 Infection

An infection that cannot be controlled or interferes with treatment in such a way that a treatment failure is likely to occur.

If cellulitis or local wound infection occurs, the Investigator may interrupt treatment in order to address this adverse event. The Investigator will treat cellulitis or local wound infection in accordance with his clinical judgment. Systemic antibiotic therapy is permitted; however, topical antimicrobials are not permitted in combination with RD1. Investigator may interrupt treatment in order to apply topical antimicrobials and resume treatment later (in the time frame of 16 weeks only)

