4.1.3 Ulcer Deterioration

Ulcer deterioration, determined by physician discretion.

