9. LOST TO FOLLOW-UP

Subjects who are lost to follow-up will be included in the primary safety analysis but only patients who complete the study will be included in the secondary objectives analysis; where wound area data are missing, imputation using LOCF (last observation carried forward) will be used.

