13. DATA ANALYSIS

13.1. Study Population and Sample size

- 13.1.1 The safety population will be all subjects who receive at least one RD1 treatment.
- 13.1.2 The intent-to-treat population (ITT) will be all subjects who complete the study.
- 13.1.3 Sample size is initially set as 60 but enrollment will be increased if necessary to compensate for drop-outs so that 60 patients complete the trial.

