13.2.1. Primary Endpoint

Efficacy- The performance of RD1 in terms of wound progress towards closure in wounds deemed suitable for treatment with RD1 (ITT population)

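### Completers are labelled ITT and withdrawn subjects are replaced, so subjects who leave for outcome-linked reasons drop out of the efficacy result

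*Protocol*

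**What the plan says.** Protocol section 13.1 names two populations. For safety: "The safety population will be all subjects who receive at least one RD1 treatment". For efficacy: "The intent-to-treat population (ITT) will be all subjects who complete the study". Section 13.2.1 assigns the primary endpoint, wound progress towards closure, to the second set. Section 13.2.2 does the same for complete closure at 16 weeks and percent area reduction. Section 9 adds that "only patients who complete the study will be included in the secondary objectives analysis", and in the same sentence provides LOCF for missing wound area.

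On replacement, section 1.2 says that "if any patients are lost to follow-up or withdrawn, enrollment will increase to compensate for loss of these subjects". Section 13.1.3 repeats this with a target of 60 subjects who finish.

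These grounds for leaving are linked to how the wound or the patient is doing:

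- Section 4.1.1: "An infection that cannot be controlled or interferes with treatment in such a way that a treatment failure is likely to occur".
- Section 4.1.3: "Ulcer deterioration, determined by physician discretion".
- Section 4.1.4: deterioration in health that leads to treatment failure.
- Appendix 5: central review of wounds that have grown by 50% or more, or risen in grade, to confirm whether the patient should be withdrawn.
- Section 8: "Noncompliance with study treatment/ offloading in a manner that interrupt treatment and delay healing, according to principal investigator judgment".

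**The concern.** The set called ITT is a completers set. Who completes depends partly on judgments about healing, made by an investigator who knows the treatment and sees the wound. A subject whose ulcer deteriorates can be stopped, left out of the closure rate and replaced by someone who may do better. The section 8 clause works the same way, but less directly: it needs noncompliance and interrupted treatment as well as delayed healing.

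As rules for stopping treatment these are reasonable. The trouble is that the same rules then decide who is counted. In a single-arm study the closure rate and area reduction are read at face value, so selection of this kind goes straight into the result. The ITT label would also lead a reader to believe that everyone treated had been counted.

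**Working it through.** **What the plan allows to be reproduced.** The 60 completers cannot be derived. The Protocol gives no significance level, power, effect size, reference rate or dropout rate. The 60 is not disputed here. All rates below are assumptions.

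**Does any text bring withdrawn subjects back?** Section 1.2 sets subjects who will complete against those lost or withdrawn, so a withdrawn subject is not a completer. The LOCF clause in section 9 stands beside the completers-only limit and does not lift it. The safety population is named only for the safety endpoint. The answer is no.

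**Noncompliance route alone.** Let

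- p = true closure rate, 0.30 to 0.60;
- c = share of subjects whose noncompliance interrupts treatment, excluding those who leave under the missed-visit rule in section 6;
- s = probability that a noncompliant non-closer is withdrawn;
- q = probability that a noncompliant eventual closer is withdrawn.

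Closure among completers, with replacement: p(1 − cq) / (1 − c[qp + s(1 − p)]).

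Closure among all treated, withdrawn counted as not closed: p(1 − cq), an error of −pcq.

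Error of the completers' rate, in percentage points, over p = 0.30 to 0.60:

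| Judgment | c = 5% | c = 10% to 30% |
|---|---|---|
| Ceiling: s = 1, q = 0 | +1.1 to +1.3 | +2.3 to +8.9 |
| Imperfect: s = 0.75, q = 0.25 | +0.5 to +0.6 | +1.1 to +4.4 |
| Unrelated to outcome: s = q | 0 | 0 |

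Example at the ceiling, p = 0.4 and c = 0.2: withdrawn share 0.2 × 0.6 = 0.12; treated 60 / 0.88 = 68.2; reported closure 0.4 / 0.88 = 45.5%, or 27.3 of 60. The same 27.3 closures over 68.2 treated give 40.0%.

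**All routes together.** If a share d of treated subjects is withdrawn and none would have closed, then with 30 of 60 completers closed:

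- d = 10%: 60 / 0.9, rounded up, is 67 treated. Reported 50.0% against 30/67 = 44.8%.
- d = 20%: 60 / 0.8 = 75 treated. Reported 50.0% against 30/75 = 40.0%.

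These are outer bounds, since some withdrawn subjects would have closed. If they closed at half the completers' rate, the all-treated figures would be 47.4% and 45.0%. The routes overlap, so figures for single routes must not be added.

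**Error of the remedy against error of the current rule**, s = 0.75 and q = 0.25, in percentage points:

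| p | c | Completers | All treated, withdrawn = not closed |
|---|---|---|---|
| 0.40 | 5% | +0.6 | −0.5 |
| 0.40 | 20% | +2.7 | −2.0 |
| 0.60 | 5% | +0.61 | −0.75 |
| 0.60 | 30% | +4.2 | −4.5 |

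Where withdrawal is unrelated to outcome (s = q = 0.5, p = 0.4, c = 20%), completers are unbiased and the remedy errs by −0.4 × 0.2 × 0.5 = −4 points.

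**The case against.** **The plan may be repaired elsewhere.** Section 13.2 refers to an SAP. But the Protocol fixes the population itself, so an SAP that followed it would carry the fault and one that did not would contradict it. It can also be said that completion is undefined and that section 4.1 speaks of stopping rather than withdrawal, so a stopped subject who attends the early termination visit might count as a completer. Section 1.2 tells against this for withdrawn subjects, and Appendix 5 speaks of withdrawal outright. The doubt is itself a reason to settle the wording.

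**Section 8 is not the culprit.** This stands. A reader might infer that section 8 lets the investigator remove poor healers at will. The text does not go that far. The phrase about delayed healing may be no more than a threshold of seriousness, section 8 asks that unnecessary withdrawals be avoided, and Appendix 13 answers inadequate offloading with further education. RD1 is applied and removed only by research staff, so noncompliance rates of 20% to 30% have no support in the documents. Deterioration under 4.1.3 and wound growth under Appendix 5 are tied more closely to outcome.

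**The size may be small.** This also stands for noncompliance alone. At 5% it is about a point or less, against a 95% half-width of about 12 points for 40% of 60 (1.96 × √(0.4 × 0.6 / 60)). The Protocol states no success threshold that such a shift could cross.

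**Two further readings go too far.** Section 1.3 mentions up to 120 or more subjects, and a reader might infer that half of those enrolled could be discarded. That figure is an enrolment plan in two phases of 40 and 80, not a dropout rate. Nor must the bias be upward: it is zero if withdrawal is unrelated to outcome.

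**Conclusion.** The point holds against sections 13.1.2 and 9, together with replacement under 1.2 and 13.1.3. As written, subjects who leave because they are doing badly leave the efficacy result too, and no text restores them. The direction favours the device if non-closers leave more often than eventual closers. That is plausible for exits defined by deterioration or expected treatment failure, but the documents do not show it.

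The amount cannot be derived from the Protocol. For noncompliance alone it is about +0.5 to +1.3 points at an assumed 5%, up to +8.9 at the ceiling with an assumed 30%, and zero if withdrawal is unrelated to outcome. The more outcome-linked exits could add to this, by an amount that depends on their unstated frequency. The change should be made because it is cheap and the label misleads, not because a large bias has been demonstrated. Confidence is medium.

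**What to change.** Leave section 8 and the stopping rules as they are.

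- **Section 13.1.2:** define the efficacy (ITT) population as everyone given one or more RD1 treatments, matching the safety population in 13.1.1.
- **Section 9:** replace the completers-only clause with one rule for every withdrawn or lost subject, whatever the ground. Take wound area from the early termination visit, or by LOCF if that visit was missed. Count the wound as not closed unless closure was documented.
- **Replacement:** it may continue, but a replaced subject stays in the denominator.
- **Completers:** report them as a sensitivity analysis, under that name.

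The cost is one line in 13.1.2 and a sentence or two in section 9. No new measurement is needed, because the visit in 1.6.3.4 already takes area, depth and the investigator's assessment of healing.

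The statistical price is a downward error, since a withdrawn subject who would have closed later counts as not closed. In some scenarios it equals or exceeds the completers' error, as the comparison above shows, but it does not favour the device. Showing both analyses lets the reader see the gap.

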9. LOST TO FOLLOW-UP

Subjects who are lost to follow-up will be included in the primary safety analysis but only patients who complete the study will be included in the secondary objectives analysis; where wound area data are missing, imputation using LOCF (last observation carried forward) will be used.

10. SUBJECT COMPLIANCE

It is essential that patients comply with the protocol. The Principal Investigator should make every effort to ensure patient compliance.

11. STUDY MONITORING

11.1. Study Records/Source Document Inspection

The data for subjects will be collected on case report forms (CRFs) and kept in a secure location in accordance with HIPAA regulations. The site investigator will allow the research team (nurses, data managers etc.), representatives of the sponsor, its monitoring team, the local IRB/EC, and other governmental regulatory agencies to monitor/audit/inspect all study records, CRFs, IRB/EC/IEC records, and corresponding portions of the site investigator's office and/or hospital medical records at regular intervals throughout the study. These monitoring/audits/inspections are conducted to verify adherence to the protocol, integrity of the data being captured on the CRFs, and compliance with applicable regulations. The sponsor requires that subjects' medical records will be maintained in a confidential manner. Study reports will not identify subjects by name or other identifiers.

11.2. Monitors

Each study site will be monitored by a qualified representative of the sponsor or any qualified monitor delegated to do so, on behalf of the sponsor. The monitor will scrutinize study data and conduct at regular intervals throughout the course of the study according to a pre-defined monitoring plan. On-site monitoring of the site investigator's facilities aids in ensuring compliance with the protocol.

Any deficiency noted during the monitoring visits will be discussed with the site investigator and corrective actions to be taken agreed upon. Should the sponsor determine at any time during the study that the site investigator is not in regulatory and/or protocol compliance, measures necessary to establish compliance will be implemented. If compliance cannot be maintained, the sponsor will suspend or terminate the study at this site.

11.3. Monitoring Plan

11.3.1 Pre-study visit

1. Assess the site's infrastructure (staff and facility) for the capability to conduct the study.
2. Evaluate Investigator and staff member's experience, qualifications, and capabilities; signed and dated CVs.
3. Financial disclosure information.

The sponsor may waive the pre-study visit in certain sites based on previous knowledge or experience with the site or personnel, or other reasons as deemed acceptable.

11.3.2 Study initiation visit

Orient the site investigator's staff involved in the study on:

1. Protocol content and procedures
2. CRF and fill-in process, including queries resolution process
3. GCP and other regulatory requirements
4. Informed consent form and process
5. AE, SAE, DRAE, safety reporting
6. IRB/EC
7. Investigational product accountability
8. Subject information: subject's identification log, subject pre-screening and screening logs, subject enrollment log, and subject study visit log
9. Study monitoring
10. Investigator's site file (ISF)
11. Report of AEs back from the sponsor to the sites (expedited safety reports)
12. Expectations from the site regarding data collection and timelines

The sponsor may choose to perform a regional investigator meeting instead of the initiation visits at each site.

11.3.3 Regular monitoring visit

1. Check on the progress of the study
2. Protocol and GCP compliance
3. Informed consent form and process
4. CRF completion, correction, source data verification
5. AE, SAE, DRAE, safety reporting
6. Investigational product
7. Investigator's study file.

(Detailed monitoring schedule to be provided at study initiation.)

11.3.4. Intermediate and final study visit; close out monitoring visit

Ensure Investigator understands the ongoing responsibilities

1. Record archival practices for source documents and CRFs after completion of the study—up to 15 years.
2. Follow-up of ongoing DRAEs—up to 30 days after completion of the study and of SAEs—until resolution.
3. Notify the sponsor in the event of Health Authority inspection.
4. Finalizing all "open" issues and complete source data verification (SDV).

12. RECORDS HANDLING AND KEEPING

12.1. Source Documents

Source documents are the initial documents in which subject data are recorded. This includes, but is not limited to, original subject files, hospital records, and original recordings/tracings from automated instruments, etc.

The sponsor allows using dedicated work sheets to serve as source documents to collect the available source data, on top of all other applicable source documents in the site.

All information captured on the CRF should be accurately supported by the source documents unless specifically approved and documented by Sponsor. For example, each subject's source documents should include (but not be limited to):

- Documenting the informed consent process
- Subject full name and identification
- Date of each study-required visit with a description of the visit and the results of each procedure that was performed
- A full and comprehensive anamnesis that will cover subject's medical history, current disease, etc.
- All concomitant procedures and medications for the screening eligibility purposes and regular visits

Any additional information relevant to the study should be included in the subject's source documents. In particular, any deviations from the study protocol or procedures should be recorded in the source documents, if noted. For example, if study-required procedures or visits are not completed or are completed outside the time frame specified in the protocol, the reasons for the departure should be explained in the source documents, or mentioned whether it was waived by the sponsor in advance. The investigator must maintain all study documentation at least 2 years after the last approval of marketing application and until there are no pending or contemplated marketing applications, or at least 2 years have elapsed since the formal discontinuation of clinical development of the investigational product. These documents should be retained for a longer period, however, if required by the applicable regulatory requirements or by an agreement with the sponsor. The sponsor should inform the investigator in writing when the trial-related records are no longer needed.

All study personnel will receive training in protecting the confidentiality of study participants and their health information. Study personnel will be asked to provide written verification of their receipt of the training. Study data will be coded with a study specific code and will not contain participant names. Informed consent forms and other documents that include names or linkages between study numbers and names will be kept in a secure locked manner with limited access. All databases will be password protected to limit unauthorized access to study data.

12.2. Data Collection Method

Data from the subject's permanent medical records (see source documentation section) will be recorded on CRFs. These CRFs will be used to transmit the information collected in the performance of this study to the clinical database either manually or by electronically.

All source data must be typewritten or filled out in ballpoint pens, accurately and promptly following each visit. The corresponding CRF should be completed so that no fields are left blank. CRFs entries corrections will be made only by crossing out (single line) incorrect data and writing in the revisions. All corrections must be initialed and dated by the individual performing/recording them. If the reason for the change is not obvious, an explanation will be recorded. Blacking out or using correction fluid or an eraser is not allowed to eliminate data. The investigator must review the CRFs for completeness and accuracy and must sign/date the forms where indicated. Signature stamps or substitutes are not acceptable. The investigator will retain originals of all source documents, subject consent forms, and study data as a permanent record.

Each set of CRFs copy should be reviewed for accuracy and completion (signatures, dates, adverse events, device-related adverse events, serious adverse events, protocol departures) and maintained in the investigator's study site.

All original data, both paper forms and electronic, will be kept in a secure place with limited access; these will be kept in secure locked cupboards at the site. Electronic files will be password protected and kept on a study computer or server to which only the study coordinator, personnel, and PIs will have access.

13. DATA ANALYSIS

13.1. Study Population and Sample size

- 13.1.1 The safety population will be all subjects who receive at least one RD1 treatment.
- 13.1.2 The intent-to-treat population (ITT) will be all subjects who complete the study.
- 13.1.3 Sample size is initially set as 60 but enrollment will be increased if necessary to compensate for drop-outs so that 60 patients complete the trial.

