1.5. Treatment Regimen

Ethics/Institutional Review Board (IRB/EC) committee approved consent is obtained prior to subject participation. The patients will be screened to determine if they meet the inclusion and exclusion criteria. The screening period lasts for up to 14 days \pm 2 days. The target ulcer will be treated with RD1. The RD1 clot is created from the subject's blood in accordance with the procedure described in the RD1 Application Protocol (Appendix 2) and according to accepted precautions guidelines. Patients will be treated with RD1 every 7 days (\pm 3 days), investigator can prolong the duration between treatments based on medical decision. Total treatment duration is up to 16 weeks or until complete healing. The RD1 should be anchored using steri-strips then covered with a primary non-adherent dressing such as Mepitel and then covered using a secondary dressing based on type of wound and amount of exudate.

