2. SELECTION CRITERIA

All of the study's inclusion and exclusion criteria must be met by Day 0 (first visit) for the subject to be eligible for the treatment phase of the study.

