2.2. Exclusion Criteria

- 2.1.10** Presence of active underlying osteomyelitis.
- 2.1.11** Patient with a proven sepsis established by a blood culture in the past 2 weeks, or confirmed active infection likely to interfere with trial, such as urine tract infection
- 2.1.12** Known malignancy in the reference wound bed or margins of the wound
- 2.1.13** Exposure of blood vessels or organs at the base of the reference wound
- 2.1.14** History of alcohol or substance abuse, within the previous 2 months
- 2.1.15** Subject has participated in another clinical trial involving a device or a systemically administered investigational study drug or treatment within 30 days of day 0 visit.
- 2.1.16** Subject is currently receiving (i.e., within the past 30 days) or scheduled to receive a medication or treatment which, in the opinion of the Investigator, is known to interfere with, or affect the rate and quality of, wound healing (e.g., systemic steroids (more than 10mg per day), immunosuppressive therapy, autoimmune disease therapy, cytostatic therapy within the past 12 months, , radiation therapy to the ulcer area, vascular surgery, angioplasty or thrombolysis).
- 2.1.17** Subject has been treated with wound dressings that include growth factors, engineered tissues or skin substitutes (e.g., Regranex®, Dermagraft®, Apligraf®, GraftJacket®, OASIS®, Primatrix®, Matristem®, etc.) within 30 days of randomization or is scheduled to receive during the study.
- 2.1.18** Subject has been treated with hyperbaric oxygen within 5 days of screening or is scheduled to receive during the study.
- 2.1.19** Wound on a patient who has a life expectancy of less than 6 months.
- 2.1.20** Cannot withdraw blood in the required amount technically.
- 2.1.21** Known coagulation problems, abnormal thrombocytes level or if heparin is given intravenously. Patients who are taking orally Coumadin, Aspirin, or Plavix (clopidogrel) will not be excluded.
- 2.1.22** Hemoglobin anemia (< 9 g/dL).
- 2.1.23** Subject has an infectious disease, such as Acquired Immune Deficiency Disease (AIDS) or HIV, Hepatitis C, Hepatitis B, Human T-lymphotropic virus or Syphilis
- 2.1.24** Women who are pregnant or currently breast feeding.

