7.2. Device-related Adverse Events

Device-related Adverse Effects (DRAEs) are previously recognized or unrecognized adverse events directly related to the use of the RD1. These DRAEs will be reported to the IRB/EC and sponsor within 24 hours of the initial discovery of the event. They are also captured in the case report forms. A DRAE that is also determined to be an SAE will also be reported separately under SAE protocol.

Subjects who develop DRAEs should be followed until the event or effect resolves or stabilizes.

All DRAEs will be collected at each visit and recorded. The following information regarding AEs will be collected:

- Description of the event
- Onset date
- Time of onset
- End date
- End time
- Severity
- Categorization of event in relation to study device (Possible, Probable, Definite; Unrelated/Unlikely categories should be moved to the SAE/AE list).
- SAE (Y/N)
- Action taken
- Outcome.

Examples of incidents that might be DRAEs include, but are not limited to:

- Complications related to venipuncture but not including lack of venous access
- Infections appearing within 2-4 days of device application.
- Bleeding at the wound site that is not related to any debridement
- Any allergic reactions
- High pain related to product application or removal

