13.2.2. Secondary Endpoints

- Safety - Determine complication rates for all adverse events compromising serious adverse events, adverse events (AEs), and device-related adverse events (DRAEs); AEs include any lack of venous access events (ITT and Safety Population)
- Efficacy - Assess the incidence of complete wound closure at 16 weeks for wounds treated with RD1 (defined as skin re-epithelialization without drainage or dressing requirements) (ITT population).
- Efficacy - Assess the wound Percent Area Reduction (PAR) (ITT population)
- Efficacy- Assess the optimal duration between applications of RD1 per wound parameter (ITT population)
- Efficacy- Assess the need of design and procedure improvements of the RD1 for specialized nursing facilities (SNF) (ITT population)
- Sub Group Analysis – asses the safety and efficacy per wound etiology (subgroup of ITT population)
- Asses the cost of RD1 procedure in SNF compared to cost of treatment before RD1 (ITT population)
- Assess wound pain compared to wound pain during treatment before RD1 (ITT population)
- Assess medical staff wound related weekly labor of wound treatment before and during RD1. (ITT population)

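### A Day 0 blood draw that ends with no RD1 applied falls outside both sets named for the safety endpoint, although lack of venous access is itself a safety event

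*Protocol*

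**What the plan says.** Protocol 13.1 defines two analysis sets. For safety (13.1.1): "The safety population will be all subjects who receive at least one RD1 treatment". For ITT (13.1.2): "The intent-to-treat population (ITT) will be all subjects who complete the study".

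The safety endpoint in 13.2.2 is assigned to these two sets and no other. Its wording ends: "AEs include any lack of venous access events (ITT and Safety Population". The same event is named in the secondary objectives in 1.1. Section 7.2 gives, as an example of a possible device-related event: "Complications related to venipuncture but not including lack of venous access". Access failure and venipuncture injury are thus two separate safety items.

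On the order of events, 1.5 says: "The RD1 clot is created from the subject's blood in accordance with the procedure described in the RD1 Application Protocol". Appendix 2 places phlebotomy at step 9, the 12-minute wait for clotting at step 16 and placement on the wound at step 20.

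Three further passages bear on a failed first draw:
- Exclusion criterion 2.1.20 (listed under 2.2): "Cannot withdraw blood in the required amount technically".
- Section 2: "All of the study's inclusion and exclusion criteria must be met by Day 0 (first visit").
- Section 8: "a subject will be withdrawn from the trial if the investigator cannot find venous access during the treatment study visits (Visits 1-16").

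**The concern.** The study procedure begins with a venipuncture, and its hazards arise before any RD1 exists. The safety set opens only once an RD1 has been received. A subject in whom the first draw fails, or is stopped because it caused harm, can therefore have a named safety event and yet belong to no set in which that event is tabulated. The completer-only ITT set cannot recover this subject. Section 9 does not either: it brings subjects lost to follow-up into the safety analysis, but says nothing of subjects who were never treated.

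At stake are two components of a secondary endpoint: the rate of lack of venous access and the rate of venipuncture complications. Both bear on whether a blood-derived dressing is practicable in nursing-facility patients. The subjects left out are selected because the draw went badly, so the omission is not neutral.

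**Working it through.** **Step 1. Set membership at Day 0.**

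| Day 0 course | RD1 received? | Safety set (13.1.1) | ITT set (13.1.2) |
|---|---|---|---|
| Draw succeeds, RD1 applied | yes | in | in if study completed |
| Draw causes harm, RD1 still applied | yes | in | in if study completed |
| Draw fails, no RD1 applied | no | out | out |
| Draw abandoned after a complication, no RD1 applied | no | out | out |

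Only the last two rows are lost. Access failures after a first RD1 are counted in the safety set.

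**Step 2. Collection versus analysis.** Adverse events are assessed on Day 0 (1.6.2). All AEs are to be recorded (7.3), device-related events go on the CRF and are reported within 24 hours (7.2), and SAEs are reported throughout participation (7.1). None of these duties depends on having received RD1. The events in the last two rows are therefore collected but not analysed.

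**Step 3. Direction.** Let n be the treated subjects, m those of them with the event, k the untreated Day 0 subjects, and j those of the k with the event. The plan reports m/n. The rate among attempted draws is (m + j)/(n + k). The count is never lower after the correction, since m + j ≥ m. The rate is higher whenever j/k exceeds m/n.
- Lack of access, where all k are failed draws: j = k, so the corrected rate is always higher (for m < n).
- Venipuncture complications: the corrected rate is higher where the draws were abandoned because of a complication. If the k subjects had no complication, only the denominator grows. With m = 2, n = 60, k = 3, j = 0, the rate is 2/63 = 3.2% against 2/60 = 3.3%, a negligible change.

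**Step 4. Size, by assumption.** The protocol gives no rate of failed first draws. Take n = 60 treated, for illustration only; in 13.1.3 the figure 60 is the target for completers, and more subjects would be treated. With j = k:

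| Later events m | As written m/60 | k = 1: (m+1)/61 | k = 3: (m+3)/63 | k = 6: (m+6)/66 |
|---|---|---|---|---|
| 0 | 0.0% | 1.6% | 4.8% | 9.1% |
| 2 | 3.3% | 4.9% | 7.9% | 12.1% |
| 5 | 8.3% | 9.8% | 12.7% | 16.7% |

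**Step 5. Status of a Day 0 failure.** Criterion 2.1.20 with section 2 lets it be read as a finding of ineligibility. Section 8 makes loss of access at Visits 1-16 a withdrawal. Section 2 calls Day 0 the first visit, whereas 1.6.3 counts the later treatment phase as weeks 1-16, so Day 0 may or may not be Visit 1. The text supports screen failure, withdrawal or adverse event, and does not choose.

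**The case against.** The strongest reply is that a safety set of treated subjects is conventional and that 2.1.20 settles the matter: a subject who cannot be bled by Day 0 never became eligible, so there is nothing to analyse. Part of this stands. The ineligibility reading is available in the text, and such a subject has no exposure to RD1 on a wound. But ineligibility does not undo harm from an attempted study venipuncture, and it sits badly with an endpoint that counts any lack of access.

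The reply continues that access is already tested at screening, since 1.6.1.20 requires blood tests. That filter is partial: subjects with laboratory results from the previous 30 days are exempt, so for them the Day 0 draw can be the first in the study.

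It may also be said that denominators for particular events belong in the SAP, which was not available here. That is fair in general. Here, however, 13.2.2 itself assigns the endpoint to two sets, and neither holds these subjects.

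Some stronger readings are tempting and are not supported:
- That everyone injured by the Day 0 draw is lost. Those who still receive RD1 are counted.
- That the events go unrecorded. Sections 7.1 to 7.3 require their collection.
- That the study stopping rule on venipuncture dropouts (4.2.3) is necessarily blind to them. It refers to patients, not to the safety population, and may include them.
- That the loss is known to be large. No rate is given, and section 8 does not expect access to be a major problem.

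**Conclusion.** The gap is real and narrow. As written, a Day 0 draw that ends without RD1 contributes to no reported safety rate, although its outcome is a named safety event. For lack of venous access the bias can only be downward. For venipuncture complications the count can only be too low, and the rate is too low where draws were abandoned because of a complication.

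The size is unknown and may be small. The range from 1.6% to 9.1% reported as 0% rests on assumed values: 60 treated subjects, no later events, and 1 to 6 Day 0 failures. No figure stated in the protocol changes.

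A reader might infer that 13.1.1 should be replaced outright by an attempted-draw population. That would go too far. It would place subjects who never had RD1 on a wound in the denominator for wound-site bleeding, infection after application, and pain on application or removal. With 6 such subjects added to 60, each of those rates would be multiplied by 60/66 = 0.91.

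**What to change.** Leave 13.1.1 as the set for wound-site and application-related events. Add to 13.1 and 13.2.2 that lack-of-venous-access and venipuncture-related events are reported among all subjects in whom a venipuncture to prepare RD1 was attempted. This includes Day 0 failures, even where the subject is then classed as ineligible under 2.1.20.

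Reconcile 2.1.20, the Day 0 wording in section 2 and the visit range in section 8, so that the status of a Day 0 failure is stated once. Which status applies is for the sponsor and investigators to decide; the attempted-draw denominator works under any of them.

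The cost is a sentence or two of protocol text, one CRF field for draw attempts and their outcome, a second safety denominator to explain in the report, and a slightly higher reported access-event rate.
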